**Figure 2. Overview of Study Procedures by Visit**

Notes: ER-AMP = extended-release dextroamphetamine; UDS = Urine Drug Screen; TLFB = Timeline Follow Back; AE/SAE = Adverse Events/Serious Adverse Events Questionnaire; C-SSRS = Columbia Suicide Severity Rating Scale; MEMS = Medication Event Monitoring System

Reward Functioning Assessment Sessions. Each Reward Functioning Assessment Session will take 2 hours over 1 visit to the ART Lab. These may be combined with treatment visits, depending on subject availability. Participants will complete 5 Reward Functioning Assessment Sessions in total (one at baseline, one in each week of treatment), so altogether these are expected to take approximately 10 hours of subject time. Eligibility to complete a Reward Functioning Assessment Session will be the absence of acute cocaine intoxication on the day of testing (based on examination of DSM-V symptoms). Participants not meeting this requirement will be re-scheduled. Current withdrawal symptoms will also be examined at each session using the Cocaine Selective Severity Assessment of Withdrawal [36], see attached. The anhedonia measures administered have been selected to tap consummatory, motivational and reward learning functions across subjective, behavioral and psychophysiological domains. See Table 1. Reward Functioning Measures for a summary. At each Reward Functioning Assessment Session, the following Reward Functioning Measures will be administered:

1. Subjective Reward Functioning Measures.

*The Snaith-Hamilton Pleasure Scale (SHAPS)* [37] is a measure of consummatory reward consisting of 14 hedonic capacity statements (e.g. "I would enjoy my favorite TV program"). See attached.

*The Temporal Experience of Pleasure Scale (TEPS)* [38] contains 18 statements measuring motivational (e.g. "I look forward to a lot of things in my life") and consummatory (e.g. "I enjoy taking a deep breath of air") reward. See attached.

2. Behavioral Reward Functioning Measures.

*The Emotional Picture Rating Task (EPRT)* [21] is a measure of consummatory reward consisting of self-reported positive, negative and aroused feelings while viewing standardized emotional pictures. Positivity and arousal ratings of positive pictures are the primary outcomes.

*The Emotional Picture Keypress Task (EPKT)* [39] is a measure of motivational reward in which subjects expend effort via keypressing to extend or reduce viewing times for emotional pictures. Keypressing to extend positive pictures is the primary outcome.

*The Effort Expenditure for Rewards Task (EEfRT)* [40] is a measure of motivational reward translated from laboratory animal tasks. On each trial subjects choose between a "hard task" requiring many keypresses but worth more money and an "easy task" requiring few keypresses but worth less money. Percent of hard task choices is the primary outcome.

*The Probabilistic Reward Task (PRT)* [41] is a measure of reward learning consisting of trials in which subjects must identify whether a cartoon face has a short or long mouth over a brief presentation. Correct identification of one category (short or long) is rewarded more often with a small monetary reward. Response bias for the rewarded category is the outcome.

3. Psychophysiological Reward Functioning Measures. During the EPRT (see above) we will record activity in the corrugator (CR; frown) muscle using electromyography (EMG), skin conductance (SC) and heart rate (HR). Positive pictures suppress corrugator activity (Larsen et al. 2003) giving a measure of

valenced facial responses to pictures. Skin conductance is enhanced to all arousing pictures, positive and negative, giving a measure of sympathetic activity to pictures. Heart rate acceleration in the later seconds of picture viewing is also sensitive to the motivation properties of pictures, with greater acceleration to more positive pictures. Together, these will give a comprehensive assessment of consummatory responses to positive pictures. EMG will be recorded using two 4mm sensors, filled with conductive gel (Biopac System Inc.), and attached to the subject's face over the corrugator using adhesive collars. Signals will be amplified and digitized using an EMG100C/MP150 system (Biopac Systems, Goleta, CA), and sampled at 1000 Hz throughout the tasks with Acqknowledge software. Magnitude of corrugator responses during positive pictures are the primary outcome. SC will be recorded using two 8mm sensors filled with isotonic gel (Biopac System Inc.) and attached to the subject's palm with an adhesive collar. Signals will be amplified and digitized using an EDA100C/MP150 system (Biopac Systems, Goleta, CA), and sampled at 1000 Hz throughout the tasks with Acqknowledge software. HR will be measured using electrocardiogram data collected with disposable Ag/AgCl electrodes placed in a standard bilateral configuration on the chest. The data will be processed through a 1-100Hz bandpass filter designed to maximize R-wave frequency.

Type of Measure	Consummatory Reward	Reward Function	Reward Learning
Subjective	SHAPS; TEPS -	TEPS - Motivational	
Behavioral	Consummatory EPRT	EPKT; EEfRT	PRT
Psychophysiological	CR EMG; SC; HR		
fMRI – note, only administered in fMRI Sub-Study	MID – Feedback; EPT	MID – Anticipation	PCfT

**Table 1.** Reward Functioning Measures by type and specific reward function

**Treatment Visits.** During the 1-week medication run-up, 4-week treatment period, and 1-week medication run-down, subjects will make thrice-weekly visits to the ART Lab (ideally Monday/Wednesday/Friday). Each treatment visit will take between 30 min and 1.5 hours depending on activities scheduled for that visit (as detailed below). All together, treatment visits are expected to take 13 hours over 18 visits. Treatment visits may be combined with Reward Functioning Assessment Sessions, fMRI Sessions, or both, depending on subject availability. Treatment visits will consist of the following activities (see *Figure 2, Overview of measures and procedures by Study Session*):

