1. Heart related problems, including stroke, heart attack and increased blood pressure and heart rate. We protect against this specific risk by requiring a full ECG and physical examination prior to enrollment in the study, with our study physician excluding individuals with contraindicating cardiovascular conditions, and by reviewing subject vitals at each visit. There have been no reported serious adverse cardiovascular events in closely monitored cocaine dependent populations [47,50,51,53–56]. Any individuals reporting symptoms of cardiovascular complications during the study will be immediately evaluated by the study physician to determine treatment needs. 2. Psychiatric problems, including mania, psychosis and aggression. We protect against this risk by excluding individuals with active psychiatric disorders aside from CUD. We additionally monitor for suicidal ideation at every study visit using a validated screening. Psychiatric adverse effects are rare, even in studies of individuals with amphetamine and cocaine use disorders [47,50,51,53–56]. Any individual showing symptoms of mania, psychosis, suicidality or aggression during the study will be immediately evaluated by the PI, a licensed clinical psychologist, to determine treatment needs. 3. Peripheral vasculopathy, including Raynaud's syndrome. Vasculopathy symptoms are generally intermittent and mild, and reverse with discontinuation of the drug. We protect against this risk by excluding individuals with other medical complications that might put them at risk for vasculopathy, and reviewing reported AEs for potential vasculopathy at each visit. There have been no reports of serious vasculopathy in studies of individuals with CUD taking this drug [47,50,51,53–56]. Any individuals reporting symptoms of vasculopathy during the study will be ~~immediately~~ evaluated by the study physician to determine treatment needs.

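### Aim 3 counts skin conductance, arousal ratings and keypressing as reward function, so a non-specific stimulant effect on arousal or motor output could be read as improved anhedonia

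*Combined protocol and SAP*

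**What the plan says.** Section 6.0 (Reward Functioning Assessment Sessions) gives scoring rules for three picture-based outcomes, and each uses positive pictures only:

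- Emotional Picture Rating Task (EPRT): "Positivity and arousal ratings of positive pictures are the primary outcomes".
- Emotional Picture Keypress Task (EPKT): "Keypressing to extend positive pictures is the primary outcome".
- Corrugator EMG: "Magnitude of corrugator responses during positive pictures are the primary outcome".

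More is collected than is scored. The EPRT records "self-reported positive, negative and aroused feelings while viewing standardized emotional pictures", and in the EPKT "subjects expend effort via keypressing to extend or reduce viewing times for emotional pictures". Section 7.0 confirms that negative pictures are shown. No contrast between picture types is defined.

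On skin conductance the same section says "Skin conductance is enhanced to all arousing pictures, positive and negative" and calls it an index of sympathetic activity. Table 1 nevertheless lists it under Consummatory Reward, with corrugator EMG and heart rate. Neither skin conductance nor heart rate has a stated scoring rule.

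Sections 3.0 and 9.0 make change in these scores over treatment the Aim 3 mediator. Sessions take place once at baseline, before any study drug, and once in each treatment week. Section 9.0 uses principal components analysis to see whether the measures reduce to consummatory, motivational and learning composites. If they do not, individual measures are used with pessimistic priors. A Bayesian probability of 80% or more that an effect exists is taken to merit further consideration.

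**The concern.** The study drug is a stimulant. Section 7.0 lists restlessness and tremors among its common effects. Skin conductance, by the protocol's own account, does not distinguish a pleasant picture from an unpleasant one. Arousal ratings confined to positive pictures cannot show whether a rise is specific to those pictures. Counts of keypresses to extend positive pictures cannot by themselves separate wanting the picture from pressing more in general.

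Aims 1 and 2 use off-drug baseline scores, so this costs them precision at most. Aim 3 is different. A non-specific effect would appear in the CM/ER-AMP arm and not in CM/PL, which is exactly the pattern the mediator is meant to detect. The trial's mechanistic claim, that the drug works by reducing anhedonia, could then gain support without any change in response to reward.

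**Working it through.** The plan states no figure for this point, so there is nothing to reproduce. The check has two parts.

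**1. Does the plan remove a non-specific effect elsewhere?**

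- Placebo control and randomization do not, because the artefact is a drug-placebo difference.
- The confounder rule in Section 9.0 covers demographic and baseline variables only; this arises after baseline.
- Principal components analysis could put arousal measures on their own component. The plan does not require that, and does not say how such a component would be used.

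**2. How large could the effect be?**

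*From the documents:*

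- 30 per Contingency Management arm and the 80% threshold.
- Seven consummatory scores: SHAPS, TEPS consummatory, EPRT positivity, EPRT arousal, corrugator EMG, skin conductance, heart rate.
- Three motivational scores: TEPS motivational, EPKT, and the effort task (EEfRT), for which "Percent of hard task choices is the primary outcome".

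*Assumed, because the documents give no values:*

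- The drug shifts only the exposed measures, by δ = 0.3, 0.5 or 0.8 SD, with no true change in reward response.
- Correlation between measures ρ = 0.2 to 0.5.
- An equal-weight composite and vague priors.

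If k of m standardized measures shift by δ, the composite shifts by

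s = (kδ/m) / √[(1 + (m − 1)ρ)/m].

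With n = 30 per arm the expected z is s·√(30/2) = s·√15. Under vague priors the 80% rule is passed when the observed z exceeds 0.842, so

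P(pass) = Φ(s·√15 − 0.842).

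With no shift this is Φ(−0.842) = 20%, the reference rate.

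Worked case, skin conductance and EPRT arousal (k = 2, m = 7, δ = 0.5):

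- ρ = 0.2: s = 0.1429/√(2.2/7) = 0.25; z = 0.99; P = 56%.
- ρ = 0.5: s = 0.1429/√(4/7) = 0.19; z = 0.73; P = 46%.

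Range over the assumptions (ρ = 0.5 to ρ = 0.2):

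| Measures shifted | δ = 0.3 | δ = 0.5 | δ = 0.8 |
|---|---|---|---|
| Skin conductance and EPRT arousal, 2 of 7: composite shift | 0.11–0.15 | 0.19–0.25 | 0.30–0.41 |
| same: 80% rule passed | 34–40% | 46–56% | 63–77% |
| EPRT arousal only, skin conductance left out, 1 of 6: 80% rule passed | 28–31% | 34–39% | 43–52% |
| EPKT only, 1 of 3 motivational: composite shift | 0.12–0.15 | 0.20–0.24 | 0.33–0.39 |
| same: 80% rule passed | 36–39% | 48–54% | 66–75% |

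Removing skin conductance alone lowers the δ = 0.5 rate from 46–56% to 34–39%. Removing EPRT arousal as well returns it to 20% under these assumptions.

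**The case against.** Much can fairly be said for the plan.

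- **The measures are meant to be read together.** The corrugator carries the valence information and skin conductance the sympathetic information; skin conductance is not offered as a stand-alone index of pleasure. That describes the design correctly, but it does not stop skin conductance from adding to a consummatory composite or being analysed singly as a consummatory measure.
- **Effort for reward is the construct.** Section 2.0 defines motivational reward as exertion of effort, so keypressing to extend positive pictures measures what it should. This stands, and is why the EPKT belongs in a repeat analysis rather than being dropped.
- **Principal components analysis or the individual-measure fallback may expose the problem.** Either might. Neither is set up to do so.
- **SHAPS, TEPS, EEfRT and the reward learning task are not scored from pictures.** True, and the calculation dilutes the shift accordingly.

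Three stronger readings are tempting but unsupported. First, a reader might infer from the listed risk of "increased blood pressure and heart rate" that the heart-rate measure is biased. It is described as acceleration in the later seconds of picture viewing, greater for more positive pictures; a higher resting rate does not by itself raise that. Second, a reader might infer that corrugator scores would falsely improve. Positive pictures suppress corrugator activity, so general muscle activation could make the reward response look worse. Third, a reader might take skin conductance and heart rate to be scored on positive pictures only. No scoring rule is stated for either.

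**Conclusion.** The point holds in a limited form and is a modest one. The Aim 3 consummatory set contains a measure that the protocol itself says does not separate positive from negative pictures, together with arousal ratings that have no comparison picture. The motivational set contains a keypress count open to motor activation. Nothing in the analysis plan is required to separate these from reward response.

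For an assumed 0.5 SD non-specific shift in skin conductance and EPRT arousal, the 80% rule on the drug-to-mediator step would be passed in about 46% to 56% of trials, against 20% with no shift. Every shift size and correlation is assumed. Direct drug action on skin conductance is inferred from its description as sympathetic activity, not stated. The figures cover only the step from drug to mediator; a positive indirect effect also needs the mediator to predict abstinence, so they are not false-mediation rates. The 80% rule marks an effect for further consideration and does not confirm it. The concern bears mainly on CM/ER-AMP against CM/PL, because the two dextroamphetamine arms share any such artefact.

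**What to change.** Before unblinding, write into Section 9.0:

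1. Skin conductance is left out of the Aim 3 consummatory score and reported by arm as an arousal control.
2. Aim 3 is repeated without EPRT arousal ratings and without the EPKT, and the indirect effect is reported both ways.
3. As a sensitivity analysis only, EPRT ratings, corrugator and EPKT are also scored as positive-minus-negative picture contrasts within session.
4. The scoring rules for skin conductance and heart rate are stated.

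All of this rescores data the design already collects, with no added participant burden. The cost is a slightly narrower consummatory score and some extra analyses.

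The contrasts should not become the main scoring. They remove only a shift that is additive and common to both picture types. They are less reliable than single-condition scores, and Section 9.0 already warns that change measures may be ill-conditioned. The documents describe no neutral pictures, so the available comparison is with negative ones, and a drug effect on negative reactivity would enter the contrast.

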
#### Treatment Activities

- 1. Medication.** At every treatment visit (run-up, run-down and treatment weeks) subjects will be administered medication and given take-home doses for intervening days. Participants in CM/ER-AMP and ER-AMP only groups will receive extended-release dextroamphetamine daily, while CM/PL subjects receive placebo. Drugs will be administered double blind in identical capsules with 50mg riboflavin total. Medication dispensing is expected to take 5min at each treatment visit. All

medication will be initiated on a gradual 1-week run-up until target dose is reached (60mg for ER-AMP). Individuals will then remain on the drug for 4 weeks, followed by a 1-week run-down, and either discharge or referral to other treatment as needed. Dextroamphetamine ER (Dexedrine Spansules) will be started at 15mg (day 1-2; 15mg am, 0mg pm), increased to 30mg (day 3; 15mg, BID), 45 mg (day 4; 30mg am, 15mg pm), and 60 mg (day 5; 30mg BID). Participants will remain at this level for 4 weeks, then be titrated down with 45 mg (day 1-2; 30mg am, 15mg pm), 30 mg (day 3; 15mg, BID), 15mg (day 4; 15mg am, 0mg pm), and finally no dose on the final day of the study (see *Figure 2*). Participants in the placebo group will follow the same dosing schedule. This same titration schedule has been used previously to safely titrate individuals with CUD to the targeted dose, maintain them for up to 12 weeks, and safely withdraw them from the drug [47]. In the event that a participant misses 3 or more days of medication (e.g. does not present for study visits despite all contact attempts), a brief re-run up will be conducted (Day 1 15mg, Day 2 30mg, Day 3 45mg, Day 4 60mg) to return them to the study dose.

2. *Contingency Management*. Participants in CM/PL and CM/ER-AMP arms will receive Contingency Management at visits thrice-weekly during the 4 treatment weeks, for a total of 12 Contingency Management sessions, per Schmitz et al. [48]. At each session, results of urine drug screens will be communicated to subjects by a trained research assistant. Research assistants will be trained using the laboratory *Timeline Followback and Contingency Management Manual* (attached), observed during initial Contingency Management administrations by the PI and subject to spot checks for adherence by the PI or other trained staff. Cocaine-negative urine drug screens will result in rewards (vouchers), starting at \$15 and increasing by \$10 for each consecutive negative urine drug screens, with bonus vouchers worth \$10 for 3 consecutive negative urine drug screens [48]. Positive urine drug screens will result in voucher omission, and reset voucher value to \$15. Participants can redeem vouchers for cash ( $\leq \$25$ ) and gift cards. Participants in the ER-AMP only group will also receive feedback on urine drug screens results at each visit during the treatment period, with no contingencies attached, to control for research assistant contact and social factors. Urine drug screen feedback and Contingency Management at each visit during treatment is expected to take approximately 5 minutes.

3. *Motivational Interviewing*. All subjects will receive two 1-h, manual-based individual Motivational Interviewing sessions in the 1st and 3rd treatment weeks to increase treatment attendance and adherence, per previous uses of the Contingency Management procedure [48]. Session 1 will focus on change motivation, change commitment, and making an abstinence plan. Session 2 will focus on personalized feedback, reassessing change commitment, and reevaluating the change plan. There will also be a 15-30min wrap-up and referral session with the therapist during the run-down week. Referrals will be tailored to the subject's needs. If the subject leaves the study sooner, every effort will be made to contact the subject and provide referrals. The PI or a graduate-level therapist will conduct the Motivational Interviewing and referral sessions. Graduate-level therapists will be trained by the PI using exercises and role-plays, and using the study *Motivational Interviewing Manual* (see attached). All therapy sessions will be recorded locally to

secure, on-campus, UIC-controlled computers using HIPAA compliant WebEx software, with session recordings uploaded to the Psychology Department's secure server and deleted after recording. Graduate level therapists will attend weekly supervision with the PI, where cases and recordings will be reviewed for compliance.

Treatment Measures. Efficacy and safety will also be monitored during treatment visits using the following measures:

1. Drug Use Measures. At every treatment visit (run-up, run-down and treatment weeks) subjects will complete urine drug screens with a Readitest 6 Cassette urine drug screen (Redwood Toxicology Laboratory), and a Timeline Follow Back of drug use since their last visit (see attached Weekly Timeline Follow Back form). Drug Use measures are expected to take 10 minutes at each treatment visit.
2. Safety Measures. At each check-in visit, a trained research assistant will take subject vital signs, review the Adverse Events Form (see attached) and Concomitant Medication Form (see attached) with the subjects, and administer the screening version of the Columbia-Suicide Severity Rating Scale (C-SSRS), a validated instrument for monitoring for suicidal ideation in clinical trials [49], see attached. Female subjects will also receive a pregnancy test every two weeks.
3. Adherence Measures. Each urine sample taken as part of Drug Use Measures will also be tested by trained research staff for riboflavin florescence. All urine samples will be collected in containers coded with subject number and visit, and disposed of immediately after testing. Medication Event Monitoring System caps that record bottle openings will be used to dispense take-home doses, with data downloaded at each treatment visit when the next dose is dispensed. Additionally, self-reported adherence will be briefly assessed by the research assistant at each visit as part of the Timeline Follow Back. Adherence measures will not require any additional subject time at treatment visits.

Total Participant Time Commitment and Compensation. Participants are compensated \$50 for the initial 3-4 hour Screening Session, which is paid separately through the separately approved screening protocol. Total subject time in study-specific procedures (i.e. excluding the initial screening) is expected to be approximately 26 hours in 20 visits to the clinic over 7 weeks for subjects in the Treatment Study. For each of the five 2 hour Reward Functioning Assessment Sessions, subjects will receive \$20, plus their winnings from the tasks, which can range from approximately \$5.00 - \$12 and are estimated at an average of \$8.00 per session. For the consent visit and each of the 18 treatment visits (through run-up, run-down and treatment) subjects will receive a base payment of \$5. Thus, base subject payment for the Treatment Study (assuming subjects attend all visits) will be \$195, plus any winnings from the tasks. Participants in the two Contingency Management groups will also have the opportunity to earn money for submission of cocaine negative urines during the 4 treatment weeks. Possible earnings range from \$0 to approximately \$880, and based on our previous trial using this same procedure, we estimate average earnings will be around \$180. All subjects will also receive either parking validation or round trip public transportation passes at

each visit to the clinic, and also can opt to have an Uber called for them for one session per week, to make it easier to attend visits.

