#### **4.3 Excluded or Vulnerable Populations**

Vulnerable Populations and Protections. Children will not be included in this research. The incidence of CUD in individuals under the age of 18 is small, so a study not specifically targeting children for recruitment is unlikely to produce usable information about this sub-group. Further, validated treatment approaches for children with substance use disorders are different than those used with adults (and proposed here). Together this makes the risk/benefit ratio for children unacceptable for this study. Pregnant women will not be included as dextroamphetamine is a Class C drug for pregnancy. Prisoners will not be included, as this is an outpatient study. Based on the demographics of individuals with CUD in the community and our experience to date, the study is likely to include individuals that are socially and economically disadvantaged or homeless. To reduce potentially coercive aspects of the study for these individuals, base compensation is not excessive. Although rewards in Contingency Management can be high, research suggests that Contingency Management is equivalently effective across individuals of different socioeconomic status, suggesting these rewards are not inequitably coercive of behavior for disadvantaged individuals [32]. The nature of the study can place individuals at risk of economic, social or legal consequences, as quantifying drug use is key to the study and the subject are expected to be illicit substance users. To address these risks we have strict confidentiality controls (see Section 13.2, Subject Confidentiality), and we carefully inform subjects about any remaining risks that cannot be mitigated. We also exclude individuals having conditions of probation or parole, as dextroamphetamine may produce positive drug tests that could be considered a violation of probation or parole, increasing the risk of legal consequences for these individuals.

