Risks During Pregnancy: Dextroamphetamine is Category C for use during pregnancy. There are no adequate and well-controlled trials to describe the full spectrum of potential toxic effects of dextroamphetamine on the fetus. No pregnant women will be permitted in study and women and men will be advised to use contraceptive measures that we provide at the clinic. Pregnancy tests will be performed at intake and every two weeks during the study. A positive pregnancy test will result in holding study medication, consultation with the study physician, and referral of the patient for medical follow up. Confirmed pregnancy will result in discontinuation of the study medication and referral for other treatment.

Risks in Combination with Other Recreational Drugs. Amphetamine can be safely co-administered with cocaine, the most likely drug combination in our subjects [55]. Previous dextroamphetamine trials [47,50,51,53] in over 200 patients with CUD have not observed hazardous interactions with recreational use of other illicit drugs, or major adverse events, despite the fact that many individuals in these studies were using cocaine and other illicit substances concurrently. Indeed, the dose of dextroamphetamine proposed (60mg) has been used for comorbid cocaine and heroin dependence in combination with methadone over 24-week period with no serious adverse events [51]. However, individuals with current use of amphetamine, >50 lifetime uses of amphetamine, or previous Amphetamine Use Disorder will be excluded, and use of other recreational drugs will be monitored at every check-in visit using breath, urine and self-report measures for potentially hazardous combinations.

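### If the urine cassette run at every treatment visit has an amphetamine strip, it would in effect unblind CM/PL v CM/ER-AMP; the protocol neither lists the analytes nor masks the reading

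*Combined protocol and SAP*

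**What the plan says.** Section 3.0 (Design Overview) calls the trial double-blind. Section 6.0 (Medication) gives the means: active drug and placebo come in identical capsules containing riboflavin. No other masking measure appears in the protocol text.

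On urine testing, Section 6.0 (Drug Use Measures) states: "At every treatment visit (run-up, run-down and treatment weeks) subjects will complete urine drug screens". The device is named only by product ("urine drug screens with a Readitest 6 Cassette urine drug screen"), and its analytes are not listed. Under Adherence Measures, "Each urine sample taken as part of Drug Use Measures will also be tested by trained research staff for riboflavin florescence", so samples are handled by study staff. Under Contingency Management, "results of urine drug screens will be communicated to subjects by a trained research assistant". The ER-AMP only group also receives feedback on its results during treatment, without vouchers.

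Four other places bear on whether amphetamine might be on the panel:

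- Section 4.3 excludes people on probation or parole "as dextroamphetamine may produce positive drug tests that could be considered a violation of probation or parole".
- Section 4.2, criterion 3, excludes current amphetamine use partly on a positive urine screen.
- Figure 2 has a single row for urine screen and Timeline Follow Back, marked from screening through run-down.
- Section 7.0, on combination with recreational drugs, says "use of other recreational drugs will be monitored at every check-in visit", with urine as one of the methods.

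**The concern.** Participants in CM/ER-AMP take an amphetamine daily and those in CM/PL do not. Current amphetamine users are excluded at entry. An amphetamine strip would therefore act as a repeated test of allocation, read on site by study staff.

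The comparison at risk is CM/PL v CM/ER-AMP. There is no placebo arm without Contingency Management, so anyone without vouchers is known from the design to be on active drug. Drug masking can matter only within the two voucher arms.

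That pair carries the medication question in Aim 3, where the mediator is change in reward functioning. Several of its components are self-reports (SHAPS, TEPS, picture ratings) or depend on voluntary effort (EPKT, EEfRT), and all of these can shift with expectancy. Attendance can shift too, and it affects both how many negative urines are submitted and who completes the weekly reward sessions. If the blind fails, a difference in the mediator could reflect knowledge of treatment as well as the drug.

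**Working it through.** The plan states no figure on this point, so there is none to reproduce. The check has two parts: whether the text closes the route, and how informative a strip would be if it were there.

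**1. Setting the sections side by side.** Section 4.2 implies that a screen able to detect amphetamine is used at entry. Figure 2 does not separate an entry panel from a treatment panel. Section 7.0 shows that urine testing during treatment is not confined to cocaine. Section 4.3 shows that the authors expect the study drug to be detectable on drug tests. None of these says that the treatment cassette contains amphetamine. Equally, none says that such a result is absent, covered, or read by someone outside the blind.

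**2. Number of readings.** Three visits a week over run-up (1 week), treatment (4) and run-down (1) give 3 × (1 + 4 + 1) = 18, which agrees with "treatment visits are expected to take 13 hours over 18 visits". The treatment weeks alone give 3 × 4 = 12, and 12 is used below.

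**3. How well readings would classify allocation.** The documents give no strip performance. Assumed here: per-visit sensitivity s from 0.50 to 0.99, false-positive rate f of 0.01 or 0.05, independent readings, and equal arms (30 v 30).

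- One reading: accuracy = (s + 1 − f)/2.
- Twelve readings, calling a participant active if at least r are positive: accuracy = [P(X ≥ r | 12, s) + P(X ≤ r − 1 | 12, f)]/2, taking the best r.

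Least favourable case (s = 0.50, f = 0.05):

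- One reading: (0.50 + 0.95)/2 = 0.725.
- Twelve readings, r = 3: P(X ≥ 3 | 12, 0.50) = 1 − (1 + 12 + 66)/4096 = 0.9807.
- P(X ≤ 2 | 12, 0.05) = 0.95^12 + 12(0.05)(0.95^11) + 66(0.05^2)(0.95^10) = 0.9804.
- The mean is 0.9806.

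| s | f | one reading | 12 readings | best r |
|---|---|---|---|---|
| 0.50 | 0.01 | 0.745 | 0.9953 | 2 |
| 0.50 | 0.05 | 0.725 | 0.9806 | 3 |
| 0.70 | 0.01 | 0.845 | 0.9998 | 3 |
| 0.70 | 0.05 | 0.825 | 0.9980 | 4 |
| 0.90 | 0.01 | 0.945 | 1.0000 | 5 |
| 0.90 | 0.05 | 0.925 | 1.0000 | 6 |
| 0.99 | 0.01 | 0.990 | 1.0000 | 7 |
| 0.99 | 0.05 | 0.970 | 1.0000 | 8 |

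With no amphetamine strip, this route gives no information and accuracy stays at 50%. Independence is a simplification: a participant who persistently skips capsules would give correlated negatives, and accuracy would then be lower than shown.

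**The case against.** The strongest reply is that the decisive fact is assumed. The protocol gives a product name, and even the number of analytes is inferred from it. Section 4.3 concerns the legal consequences of drug tests, not the study cassette. The Section 4.2 screen belongs to entry, and screening runs under a separately approved protocol. In Section 7.0 the monitored drugs are described as other ones, straight after amphetamine users are excluded, so amphetamine may not be meant. The attached Timeline Follow Back and Contingency Management manual was not available and may contain a safeguard. All of this stands. It limits the point to an open risk, but it does not close the route, because the protocol text contains no safeguard.

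Several stronger readings are tempting and are not supported:

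- **That the blind is shown to be broken.** No section places an amphetamine strip on the cassette.
- **That participants are told an amphetamine result.** The results tied to vouchers are cocaine results; otherwise participants on active drug could not earn vouchers as intended.
- **That the same people read the cassette and run the reward sessions.** The text refers to a trained research assistant and to trained staff, and does not say who reads the cassette.
- **That 50 of 80 participants over 18 visits measures the problem.** The drug status of the 20 in ER-AMP only is already evident from the design. The relevant scale is 30 v 30 with 12 treatment-week readings.
- **That every reading separates the arms.** Under the assumed range, one reading is right 72.5% to 99% of the time.

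It is also fair that the primary clinical outcome is a cocaine urine result. Section 10.0 says that behavioural and psychophysiological data are captured by computer, and that psychophysiology is scored by independent raters. This protects the recording and scoring. It does not protect questionnaire answers or voluntary effort if a participant knows or suspects the allocation. Vital signs and side effects, reviewed at each visit, may already hint at allocation, so the added masking from covering a strip cannot be quantified from the documents.

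**Conclusion.** The point holds as a conditional blinding risk. The protocol claims a double blind, describes only identical capsules, and runs a cassette of unstated content at every treatment visit while acknowledging that the study drug can turn drug tests positive. If the cassette includes amphetamine, 12 treatment-week readings would identify allocation in CM/PL v CM/ER-AMP with about 98% accuracy or better, under the assumed sensitivity, false-positive rates and independence. If it does not, the effect is nil.

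The exposure is to staff who see the cassette, and to participants only if they see it or are told. It falls mainly on the self-report and effort-based reward measures in the Aim 3 mediator, and on retention. The cocaine urine outcome and psychophysiology are less exposed. The change is worth making because it costs very little and does no harm if the strip proves absent.

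**What to change.** In Section 6.0 (Drug Use Measures), list the analytes on the treatment-phase cassette. Require either that it has no amphetamine strip or that the strip is covered before blinded staff or participants can see it. If an amphetamine result is wanted for the monitoring described in Section 7.0, have it read and held by someone outside the blind. Under Contingency Management, state that only the cocaine result is communicated to participants, in the ER-AMP only group as well. If the manual already provides this, one sentence in Section 6.0 citing it is enough.

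The cost is a different cassette or an opaque cover, a line in the manual and, if used, an unblinded reader. The downside is that blinded staff would no longer see non-study amphetamine use in CM/PL directly; it would have to come from self-report or the unblinded reader. In the active arms little is lost, because a strip could not tell study drug from other amphetamine.
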